6.7.2 Eligibility criteria

Inclusion criteria

- Age ≥18 years,
- Ability to give informed consent,
- Meets the clinical American College of Rheumatology (ACR)/European League Against Rheumatism (EULAR) classification criteria for gout [26],

Page 34 of 71 Treat to target in gout Protocol Final Version 1.1 date 29 May 2019

Table 8 ACR/EULAR classification criteria for gout

ACR/EULAR classification criteria for gout: A score of 7 or more is sufficient to classify the participant as having gout History of at least one episode of swelling, pain, or tenderness in a peripheral joint/bursa should be present before the classification criteria are applied Clinical classification criteria Pattern of joint/bursa involvement during episodes Joint/bursa other than ankle, midfoot or 1st MTPJ (or involvement in a polyarthritis) Ankle OR midfoot (as part of monoarticular/oligoarticular episode without 1st 1 1 <		
History of at least one episode of swelling, pain, or tenderness in a peripheral joint/bursa should be present before the classification criteria are applied Clinical classification criteria Pattern of joint/bursa involvement during episodes Joint/bursa other than ankle, midfoot or 1st MTPJ (or involvement in a polyarthritis) Ankle OR midfoot (as part of monoarticular/oligoarticular episode without 1st 1 1st MTPJ (as part of monoarticular or oligoarticular episode) 2 How many characteristics during episode(s)? Erythema overlying joint (reported or observed); can't bear touch or pressure to joint; great difficulty with walking or inability to use joint. No characteristics 1 Two characteristics 2 Three characteristics 3 How many episodes with the following time-course? ≥2 time course symptoms, regardless of anti-inflammatory use: (1) Time to maximal pain < 24 hours; (2) Resolution of symptoms in ≤14 days; (3) Complete resolution (to baseline level) between symptomatic episodes. No typical episode 1 Recurrent typical episodes 2 Evidence of tophus. Draining or chalk-like subcutaneous nodule, located in typical locations: joints, ears, olecranon bursae, finger pads, tendons (e.g., Achilles). Absent 0 Present 4 Serum urate <a href="https://www.link.com/lin			

joint/bursa should be present before the classification criteria are applied
Clinical classification criteria
Pattern of joint/bursa involvement during episodes
Joint/bursa other than ankle, midfoot or 1st MTPJ (or involvement in a
polyarthritis)
Ankle OR midfoot (as part of monoarticular/oligoarticular episode without 1st
MTPJ)
1st MTPJ (as part of monoarticular or oligoarticular episode) 2
How many characteristics during episode(s)? Erythema overlying joint
(reported or observed); can't bear touch or pressure to joint; great difficulty
with walking or inability to use joint.
No characteristics 1
Two characteristics 2
Three characteristics 3
How many episodes with the following time-course?
≥2 time course symptoms, regardless of anti-inflammatory use:
(1) Time to maximal pain < 24 hours; (2) Resolution of symptoms in ≤14
days; (3) Complete resolution (to baseline level) between symptomatic
episodes.
No typical episodes 2
Evidence of tophus. Draining or chalk-like subcutaneous nodule, located in
typical locations: joints, ears, olecranon bursae, finger pads, tendons (e.g.,
Achilles).
Absent 0
Present 4
Serum urate
km of serum urate 240 or < 360 µmol/L -4 ≥ 240 or < 480 µmol/L 2 ≥ 480 or < 600 µmol/L 3	A score of 7 or more is sufficient to classify the participant as having gout	
Pattern of joint/bursa involvement during episodes 0 Joint/bursa other than ankle, midfoot or 1st MTPJ (or involvement in a polyarthritis) 0 Ankle OR midfoot (as part of monoarticular/oligoarticular episode without 1st 1 1 MTPJ (as part of monoarticular or oligoarticular episode) 2 How many characteristics during episode(s)? Erythema overlying joint (reported or observed); can't bear touch or pressure to joint; great difficulty with walking or inability to use joint. No characteristics More characteristics 0 One characteristics 1 Two characteristics 1 Two characteristics 1 Two characteristics 2 How many episodes with the following time-course? 2 ≥2 time course symptoms, regardless of anti-inflammatory use: 11 (1) Time to maximal pain < 24 hours; (2) Resolution of symptomatic episode		
Joint/bursa other than ankle, midfoot or 1st MTPJ (or involvement in a polyarthritis) 0 Ankle OR midfoot (as part of monoarticular/oligoarticular episode without 1st MTPJ) 1 1st MTPJ (as part of monoarticular or oligoarticular episode) 2 How many characteristics during episode(s)? Erythema overlying joint (reported or observed); can't bear touch or pressure to joint; great difficulty with walking or inability to use joint. 0 One characteristics 0 One characteristics 1 Two characteristics 2 How many episodes with the following time-course? 2 22 time course symptoms, regardless of anti-inflammatory use: 1 (1) Time to maximal pain < 24 hours; (2) Resolution of symptoms in ≤14 days; (3) Complete resolution (to baseline level) between symptomatic episodes		
polyarthritis) Ankle OR midfoot (as part of monoarticular/oligoarticular episode without 1st MTPJ) 1 1st MTPJ (as part of monoarticular or oligoarticular episode) 2 How many characteristics during episode(s)? Erythema overlying joint (reported or observed); can't bear touch or pressure to joint; great difficulty with walking or inability to use joint. 0 With walking or inability to use joint. No characteristics 0 One characteristics 1 1 Two characteristics 2 1 Two characteristics 2 3 How many episodes with the following time-course? ≥ ≥2 time course symptoms, regardless of anti-inflammatory use: 1 (1) Time to maximal pain < 24 hours; (2) Resolution of symptoms in ≤14	Pattern of joint/bursa involvement during episodes	
MTPJ)1st MTPJ (as part of monoarticular or oligoarticular episode)2How many characteristics during episode(s)? Erythema overlying joint (reported or observed); can't bear touch or pressure to joint; great difficulty with walking or inability to use joint.0No characteristics0One characteristics1Two characteristics1Two characteristics3How many episodes with the following time-course? ≥ 2 time course symptoms, regardless of anti-inflammatory use: (1) Time to maximal pain < 24 hours; (2) Resolution of symptoms in <14 days; (3) Complete resolution (to baseline level) between symptomatic episodes.0No typical episodes0One typical episodes1Recurrent typical episodes2Evidence of tophus. Draining or chalk-like subcutaneous nodule, located in typical locations: joints, ears, olecranon bursae, finger pads, tendons (e.g., Achilles).0Serum urate240 or < 360 µmol/L		0
How many characteristics during episode(s)? Erythema overlying joint (reported or observed); can't bear touch or pressure to joint; great difficulty with walking or inability to use joint. No characteristics 0 One characteristics 1 Two characteristics 1 Two characteristics 2 1 Two characteristics 3 How many episodes with the following time-course? ≥2 ≥2 time course symptoms, regardless of anti-inflammatory use: 1 (1) Time to maximal pain < 24 hours; (2) Resolution of symptoms in ≤14 days; (3) Complete resolution (to baseline level) between symptomatic episodes. 0 No typical episodes 0 Cone typical episodes 2 Evidence of tophus. Draining or chalk-like subcutaneous nodule, located in typical locations: joints, ears, olecranon bursae, finger pads, tendons (e.g., Achilles). 0 Present 4 Serum urate < 240 µmol/L	MTPJ)	1
How many characteristics during episode(s)? Erythema overlying joint (reported or observed); can't bear touch or pressure to joint; great difficulty with walking or inability to use joint. No characteristics 0 One characteristics 1 Two characteristics 1 Two characteristics 2 1 Two characteristics 3 How many episodes with the following time-course? ≥2 ≥2 time course symptoms, regardless of anti-inflammatory use: 1 (1) Time to maximal pain < 24 hours; (2) Resolution of symptoms in ≤14 days; (3) Complete resolution (to baseline level) between symptomatic episodes. 0 No typical episodes 0 Cone typical episodes 2 Evidence of tophus. Draining or chalk-like subcutaneous nodule, located in typical locations: joints, ears, olecranon bursae, finger pads, tendons (e.g., Achilles). 0 Present 4 Serum urate < 240 µmol/L	1st MTPJ (as part of monoarticular or oligoarticular episode)	2
with walking or inability to use joint.No characteristics0One characteristics1Two characteristics2Three characteristics3How many episodes with the following time-course? ≥2 time course symptoms, regardless of anti-inflammatory use: (1) Time to maximal pain < 24 hours; (2) Resolution of symptoms in ≤14 days; (3) Complete resolution (to baseline level) between symptomatic episodes.0No typical episodes0One typical episodes0One typical episodes1Recurrent typical episodes2Evidence of tophus. Draining or chalk-like subcutaneous nodule, located in typical locations: joints, ears, olecranon bursae, finger pads, tendons (e.g., Achilles).0Absent0Present4Serum urate< 240 µmol/L		
One characteristics 1 Two characteristics 2 Three characteristics 3 How many episodes with the following time-course? ≥2 time course symptoms, regardless of anti-inflammatory use: (1) Time to maximal pain < 24 hours; (2) Resolution of symptoms in ≤14 days; (3) Complete resolution (to baseline level) between symptomatic episodes.		
Two characteristics2Three characteristics3How many episodes with the following time-course? \geq 2 time course symptoms, regardless of anti-inflammatory use: (1) Time to maximal pain < 24 hours; (2) Resolution of symptoms in <14 days; (3) Complete resolution (to baseline level) between symptomatic episodes.0No typical episodes0One typical episodes1Recurrent typical episodes2Evidence of tophus. Draining or chalk-like subcutaneous nodule, located in typical locations: joints, ears, olecranon bursae, finger pads, tendons (e.g., Achilles).0Present4Serum urate $< 240 \ \mumol/L$ -4 $\geq 240 \ or < 360 \ \mumol/L$ 0 $\geq 360 \ or < 480 \ \mumol/L$ 2 $\geq 480 \ or < 600 \ µmol/L$ 3	No characteristics	0
Three characteristics 3 How many episodes with the following time-course? ≥2 time course symptoms, regardless of anti-inflammatory use: (1) Time to maximal pain < 24 hours; (2) Resolution of symptoms in ≤14	One characteristics	1
How many episodes with the following time-course?≥2 time course symptoms, regardless of anti-inflammatory use: (1) Time to maximal pain < 24 hours; (2) Resolution of symptoms in ≤14 days; (3) Complete resolution (to baseline level) between symptomatic episodes0No typical episodes00One typical episodes11Recurrent typical episodes2Evidence of tophus. Draining or chalk-like subcutaneous nodule, located in typical locations: joints, ears, olecranon bursae, finger pads, tendons (e.g., Achilles).0Present4Serum urate< 240 µmol/L	Two characteristics	2

Serum urate < 240 µmol/L -4 ≥ 240 or < 360 µmol/L	Absent	0
 < 240 µmol/L -4 ≥ 240 or < 360 µmol/L 0 ≥ 360 or < 480 µmol/L 2 ≥ 480 or < 600 µmol/L 3 	Present	4
≥ 240 or < 360 µmol/L 0 ≥ 360 or < 480 µmol/L 2 ≥ 480 or < 600 µmol/L 3	Serum urate	
≥ 360 or < 480 µmol/L 2 ≥ 480 or < 600 µmol/L 3		-4
≥ 480 or < 600 µmol/L 3	≥ 240 or < 360 µmol/L	0
≥ 600 4		3
	≥ 600	4

- ≥1 flare of gout in the previous 12 months, and
- Serum urate ≥360 µmol/L regardless of current ULT

Exclusion criteria

- Previous allopurinol side-effects that contraindicate its prescription,
- Dementia, severe enduring mental illness i.e. mental health illness that makes receiving the study information and initial screening questionnaire from GP a stressful experience,

Page 35 of 71 Treat to target in gout Protocol Final Version 1.1 date 29 May 2019

- Unable to comply with study procedures,
- Life expectancy less than 12 months,
- Cancer treatment, i.e. surgery, radiotherapy, or chemotherapy in the previous 12 months,
- Solid organ transplant,
- Cirrhosis,
- Autoimmune rheumatic disease i.e. rheumatoid arthritis, psoriatic arthritis, systemic lupus erythematosus, connective tissue diseases, vasculitis, giant cell arteritis, polymyalgia rheumatica, inflammatory arthritis associated with inflammatory bowel disease, reactive arthritis, ankylosing spondylitis,
- Inflammatory bowel disease
- Current long-term daily oral corticosteroid treatment defined as continuous use for ≥30 days or current immunosuppressive treatments,
- Stage 4/5 CKD i.e. eGFR < 30 ml/min,
- Pregnant, breast feeding or planning to become pregnant in the next 4 years.

6.7.3 Removal of participants from therapy or assessments/participant withdrawal

Study participants will be allowed to discontinue treat-to-target ULT if they:

[1] experience side-effects from the treat-to-target ULT protocol and are unwilling to continue on it, ,

[2] develop a temporary or permanent contra-indication to ULT, such as pregnancy, terminal illness, or

[3] wish to discontinue treat-to-target ULT without specifying a reason.

However, every attempt will be made to keep them in the study. If they agree to continue in the study, they will be invited to attend research assessment visits and provide outcome data.

Intent to withdraw from the study:

If a participant indicates a wish to withdraw, the participant will be requested to at least permit primary outcome data to be collected (ideally at the end of the participant's follow-up period), ensuring that enough data are recorded to support the planned analysis. Phone-calls, and letters to the participant will be used for re-contacting and reminding non-responders and nonattendees.

Study participants will be withdrawn from the study if:

- [1] consent is withdrawn,
- [2] at the participants' own discretion, or
- [3] at the discretion of the Chief Investigator.
 - The participants will be made aware that withdrawing from the study will not affect their future care, and that abrupt termination of study treatment does not affect their safety.

Treat to target in gout Protocol Final Version 1.1 date 29 May 2019

- Participants who withdraw from the study will have data on the date of withdrawal and reason of withdrawal collected where possible.
- Participants will be made aware (via the PIS and consent form) that should they withdraw, the data collected to date cannot be erased or destroyed and will still be used in the final analysis.
- •

Enrolled participants who are not yet randomized can be replaced (though keeping their trial ID), but participants who withdraw after randomization will not be replaced.

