A&E attendance for gout flare (number, admission and discharge dates)

Side-effects to ULT (specify event, dates)

Side-effects to flare prophylaxis (specify events, dates)

Side-effects to flare treatment (specify events, dates)

7.8 Data collected by study participants:

Electronic acute gout flare diary: A mobile phone text-messaging system will be used to collect data on occurrence and severity of gout flares.

Text message system:

- Participants will receive a welcome text message at the baseline visit after randomisation to confirm their telephone number, welcome them to the study and advise them that they will receive SMS messages going forward.
- Study participants will initiate the text-messaging service by texting the word "gout" when they experience a flare. If they forget to text on the first day, they can still text "gout" at a later date.
- The messaging system will send short text messages enquiring about pain severity (0–10 numerical rating scale), presence of warm joint, and swollen joint [47]. This will be used to classify self-reported gout flares as meeting the criteria for a flare of gout [47]. For a flare to be present, the episode should meet the flare definition criteria, i.e. at least 3 of the following four: pain severity >3/10, presence of warm

Page 45 of 71 Treat to target in gout Protocol Final Version 1.1 date 29 May 2019

joint, swollen joint, and self-reported flare [47]. A single reminder will be sent for non-response.

- On day 1 of self-reported gout flare the messaging system will ask participants how long they have had the flare for, and send a message asking participants to complete EQ-5D-5L in the paper diary within next 48 hours.
- The messaging system will then send daily text messages enquiring about pain severity on a 0–10 numerical rating scale (NRS) each morning for up to 7 days, with a reminder to answer the question if needed. This suite of messages will be discontinued if the participants responds with a score of 0 or 1 on 2 consecutive days. The pain numerical rating scale is endorsed by Outcome Measures in Rheumatology Clinical Trials for measuring the severity of flares of gout [48].

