- After 7 days, or if there are two days with NRS 0 or 1, the participant will receive a thank-you text, and, a reminder to complete the questions regarding wellbeing during gout flare and gout concern during flare domains of GIS, healthcare utilization during gout flare and date the gout flare resolved in a paper diary.
- To mitigate the risk of a single flare being counted as multiple flares, a flare will be defined as an incident flare if there is at least a 48-hour time period between the end of the previous flare reporting period and the start of next flare. If the interval between is smaller than 48 hours, they will be regarded as a single episode. Flares with no reported daily pain NRS will be excluded from analysis of secondary outcomes e.g. flare severity and duration.
- If the participant forgets to text when the flare is occurring, he or she will be able to contact the research team by phone during weekday office hours to report the date of onset and end of the most recent gout flare. The researcher will elicit information about pain severity (0–10 NRS), presence of warm joint, swollen joint, to classify self-reported gout flares as meeting the criteria for gout flare [47]. Daily pain severity and EQ-5D-5L will not be available for such episodes.

Paper diary: A paper diary will be available for those who do not have a mobile phone or do not wish to use text-messages.

Reminders: As study participants can forget completing the gout flare diary, they will receive a text or a letter (if they do not have a mobile phone), every 2 months, reminding them to complete the gout flare diary, and, if they had a flare for which they did not complete the flare diary, they will be encouraged to phone dedicated research staff in the research team to provide these data.

Health related QoL during gout flares: To account for QoL during gout flares, the participants will complete the EQ-5D-5L once within the first 48 hours of onset of each gout flare. The collection of EQ-5D-5L also allows us to bring health status during gout flare into overall cost-utility analysis.

The wellbeing during gout flare and gout concern during flare sub-scales of the GI S, which captures disease specific QoL during the most-recent gout flare, will be completed within 2 days of complete resolution of the acute gout flares.

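### For participants who wish to withdraw, section 6.7.3 prefers collecting the primary outcome at the end of follow-up and names no method, although flares are otherwise recorded episode by episode with two-monthly reminders

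*Protocol*

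**What the plan says.** **Withdrawal.** Protocol section 6.7.3 says that someone who wishes to withdraw will be "requested to at least permit primary outcome data to be collected (ideally at the end of the" participant's follow-up period). It names no instrument for this. Phone calls and letters are to be used to re-contact people who do not respond or attend. The same section says that, after withdrawal, "the data collected to date cannot be erased or destroyed and will still be used in the final analysis".

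**How a flare is counted.** Section 7.8 works per episode: "For a flare to be present, the episode should meet the flare definition criteria, i.e. at least 3 of the following four", the four being pain above 3/10, a warm joint, a swollen joint and self-report. Two episodes are separate only if there is "at least a 48-hour time period between the end of the previous flare reporting period and the start of next flare".

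**Routine collection.** Flares are texted as they occur, or written in a paper diary. Table 11 (section 7.6) shows the diary given at baseline and collected at years 1 and 2. A participant who did not text at the time may "contact the research team by phone during weekday office hours to report the date of onset and end of the most recent gout flare". In that call, "The researcher will elicit information about pain severity (0–10 NRS), presence of warm joint, swollen joint". On reminders, the section says: "As study participants can forget completing the gout flare diary, they will receive a text or a letter", every two months, and anyone with an unrecorded flare is encouraged to phone. Section 8.2 likewise asks participants to phone about any flares not reported at all.

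**The concern.** The outcome depends on details that fade: when each flare began and ended, how bad the pain was, and whether the joint was warm and swollen. The routine system keeps the recall interval short, with texts at the time of the flare and a prompt every two months. For participants who wish to withdraw, section 6.7.3 states the opposite preference. Someone who leaves at month 6 would ideally be asked at month 24 about the 18 months between.

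The protocol does not describe how several flares over such an interval would be elicited, dated and classified at one contact. An analysis plan cannot recover dates and symptoms that were never recorded. If flares after withdrawal are under-reported, and more people withdraw from one arm, the rate ratio moves. The split into months 1–12 and 13–24 (section 6.1.2) would also be less certain for that period.

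**Working it through.** **1. The plan's own allowance.** Section 8.6 needs 186 per group and allows 20% loss: 186 / (1 − 0.20) = 232.5, so 233. This reproduces. Twenty per cent of 233 is 46.6, about 47 people per arm. That is a ceiling for this point, because many people lost to follow-up would give no late report.

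**2. What is affected.** Flares before withdrawal keep their real-time dates and scoring, so only time after withdrawal counts. If withdrawals are spread evenly over 24 months (assumption), a participant who withdraws loses half of follow-up on average.

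**3. Formula.** With w the proportion withdrawing and r the share of later flares that a late contact captures:

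observed share of an arm's flares = 1 − w × 0.5 × (1 − r)

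The protocol gives neither r nor withdrawal by arm. I take r = 0.4, 0.6 and 0.8 as assumptions, equal in both arms.

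**4. One arm, w = 20%.** The share is 0.94, 0.96 and 0.98, so the count is 2 to 6% low.

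**5. Multiplier on the rate ratio** (intervention share / control share):

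| Withdrawal, intervention v control | r = 0.4 | r = 0.6 | r = 0.8 |
|---|---|---|---|
| 20% v 20% | 1.000 | 1.000 | 1.000 |
| 25% v 15% | 0.925/0.955 = 0.969 | 0.950/0.970 = 0.979 | 0.975/0.985 = 0.990 |
| 25% v 10% | 0.925/0.970 = 0.954 | 0.950/0.980 = 0.969 | 0.975/0.990 = 0.985 |
| 15% v 25% | 1.032 | 1.021 | 1.010 |
| 10% v 25% | 1.049 | 1.032 | 1.015 |

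The last two rows reverse the imbalance. The shift is then about the same size in the other direction.

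**6. Against the planned effect.** The largest shifts turn the planned 0.650 into 0.650 × 0.954 = 0.620 or 0.650 × 1.049 = 0.682.

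**7. Against sampling error.** With the section 8.6 inputs (means 3.54 and 2.30, dispersion 1.50), the variance of the log rate ratio is (1/3.54 + 1/2.30 + 2 × 1.50)/n = 3.717/n. At n = 186 the standard error is 0.141. The shifts in the 25% v 15% and 25% v 10% rows run from ln(0.990) = −0.010 to ln(0.954) = −0.048, which is 0.07 to 0.34 standard errors. At the largest, a 5% two-sided error rate becomes about 6.3%. If all 233 per arm contribute a count, the standard error is 0.126, the largest shift is 0.38 standard errors, and the error rate is about 6.6%.

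**The case against.** The strongest defence is that section 6.7.3 only expresses the usual intention-to-treat aim: do not cut the outcome short at withdrawal. On that reading, collection runs until the end of follow-up, and the clause about having enough data for the planned analysis fits it. The wording allows this. But it says at the end, names no method, and is followed by re-contact by phone and letter, so a site could reasonably follow it as a late contact. If continued collection is meant, the text should say so.

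A reader might go further and infer that one recalled total replaces the real-time count, and that the flare definition cannot be applied to it. The documents do not support that:

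- Data recorded before withdrawal are kept, and no single total is mentioned.
- A paper diary kept as flares occur is already collected at years 1 and 2.
- In the phone route, the researcher asks about pain, warmth and swelling and takes dates, so the definition can be applied after the event. That route is described for the "most recent" flare in the sense of "report the date of onset and end of the most recent gout flare", but the reminder text and section 8.2 invite reports of any unreported flare.

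Lower accuracy over a long interval is what remains.

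A reader might also infer bias in favour of treat-to-target, because titration visits and side-effects could drive withdrawal. No figure in the protocol shows this. Section 6.7.3 separates stopping treatment from leaving the study and asks those who stop to stay for assessment. In an open trial, control participants may leave too. This objection stands, and no direction is claimed.

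**Conclusion.** The point holds in a limited form. For flares after withdrawal, section 6.7.3 states a preference that fits poorly with the way section 7.8 measures the outcome, and it gives no method. Followed literally, it would yield poorer data than keeping people on the existing text or diary.

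The numerical consequence is small: about 1 to 5% on the rate ratio, in either direction. This rests on assumptions outside the protocol: even timing of withdrawal, 40 to 80% recall, and a 10 to 15 percentage-point difference in withdrawal between arms. It also takes every withdrawer to give a late report. With equal withdrawal and recall the bias is nil. It does not threaten the planned comparison, but the wording can be improved at little cost.

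**What to change.** In section 6.7.3, replace the end-of-follow-up preference with an ordered request:

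1. Offer flare-only follow-up to month 24, using the existing flare text or paper diary and the two-monthly reminder, with no other study procedures.
2. If this is declined, record flares up to the withdrawal date and seek permission for GP-record extraction. Section 7.7 already extracts dated flare consultations, though these miss flares that led to no contact and list no symptom criteria.
3. Failing that, make one contact at the end of follow-up, and flag such counts as retrospectively recalled.

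How partial follow-up and flagged counts enter the model is for the SAP.

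The cost is a change of wording in the protocol and the withdrawal form; the text system, diary and reminders already exist. The downside is slightly more contact with people who wish to withdraw, and some may decline it.
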